A network meta-analysis (2017) about dressings and topical agents for treating pressure ulcers (Review) of data from 39 studies (evaluating 21 dressings and topical agents for pressure ulcers) concluded that consequently we are unable to determine which dressings or topical agents are the most likely to heal pressure ulcers and more research is needed to determine whether particular dressings or topical agents improve the probability of healing of pressure ulcers [29]. Moreover Boyko et al. (2018), in a review of the current management of pressure ulcers, stated that despite many treatments available, none of them is superior to the other, and pressure ulcers remain a debilitating and costly issue. They recommended additional research to develop products more effective in preventing and treating pressure ulcers [20].

The incidence of pressure ulcers will possibly grow rapidly in the future due to increased life expectancy and aging. However, although various methods are used to treat pressure ulcers, no standard therapy has previously been established. After searching the literature there no studies done before to compare the effects of zinc oxide versus MEBO in treatment of second stage pressure ulcer and because there is no standardization for this practice this clinical trial will be conducted to compare the effects of zinc oxide versus MEBO in treatment of second stage pressure ulcer and determine which one is superior to other.

OBJECTIVES:

The **primary objective** of this study is to:

- 4 -

Short Title: Impact of using Zinc Oxide versus Moist Exposed Wound Ointment (MEBO) in treatment of second stage pressure ulcer: A randomized control clinical trial.

Version: 5.0 (Dated 28-Mar-2023)

Effective date: 29-Mar-2023

Expiration date: 29-Mar-2024

Impact of using zinc oxide versus Moist Exposed Wound Ointment (MEBO) in treatment of second stage pressure ulcer: A randomized control clinical trial.

- To evaluate the efficacy of using zinc oxide versus moist exposed wound ointment in treatment of second stage pressure ulcer.

Secondary Objectives

- To determine the recovery time for both ointments.

Objective measures

For the primary objective

Wound healing will be assessed by using Bates–Jensen Wound Assessment Tool (BWAT) daily for both treatments.

For the secondary objective

The duration of treatment will be record at the assessment sheet so Recovery time will be determined from this sheet.

Research Design:

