- Open label randomized control clinical trial study with a pilot study-using questionnaire.

Inclusion Criteria:

- Subjects ≥ 18
- Willing to participate.
- KAMC cases in medical ward, neuroscience ward, and intensive care unit.
- Newly cases diagnosed with second stage pressure ulcer according to the European pressure ulcer advisory panel/national pressure ulcer advisory panel (NPUAP) guidelines.

Exclusion Criteria:

- 5 -

Short Title: Impact of using Zinc Oxide versus Moist Exposed Wound Ointment (MEBO) in treatment of second stage pressure ulcer: A randomized control clinical trial.

Version: 5.0 (Dated 28-Mar-2023)

Effective date: 29-Mar-2023

Expiration date: 29-Mar-2024

Impact of using zinc oxide versus Moist Exposed Wound Ointment (MEBO) in treatment of second stage pressure ulcer: A randomized control clinical trial.

- Subjects under 18
- Not consenting to participate
- Patients with suspected hypersensitivity reactions to any of the topical formulation's ingredients.
- Either a category III or IV pressure ulcer.
- Evidence of deep tissue injury (exudative drainage, purple or maroon localized area of discolored intact skin or blood-filled blister due to pressure damage).
- Signs of wound infection (pus draining from the ulcer, a foul-smelling odour, tenderness, heat and increased redness in the surrounding skin and fever).
- Patients who undertaking other therapies that could affect healing, such as corticosteroids, radiation therapy, or chemotherapy for cancer.
- Heavy smoking (more than 20 cigarettes a day).
- Concomitant chronic disease (e.g., diabetes mellitus or frank vascular disease such as Buerger's disease).
- Patients who unable to continue the study because of death, discharge, or change in the care setting.

Randomization

Simple randomization method will be used through electronic randomization. The randomization list was generated electronically through R using the Random Allocation Rule by research center member who did not directly participate in trial recruitment and enrolment. Research center member will define

- 6 -

Short Title: Impact of using Zinc Oxide versus Moist Exposed Wound Ointment (MEBO) in treatment of second stage pressure ulcer: A randomized control clinical trial.

Version: 5.0 (Dated 28-Mar-2023)

Effective date: 29-Mar-2023

Expiration date: 29-Mar-2024

Impact of using zinc oxide versus Moist Exposed Wound Ointment (MEBO) in treatment of second stage pressure ulcer: A randomized control clinical trial.

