The sample size for the study calculated using the following formula based on the study of Li et al (2017).

$$\text{Sample size (n)} = \frac{p_1(1-p_1) + p_2(1-p_2)}{(p_1-p_2)^2} * C$$

n = Sample size for one group that we need to find out

p1 and p2 = Proportion of two groups

C = Standard value for the corresponding level of α and β selected for the study $(0.84+1.96)^2$.

- 9 -

Short Title: Impact of using Zinc Oxide versus Moist Exposed Wound Ointment (MEBO) in treatment of second stage pressure ulcer: A randomized control clinical trial.

Version: 5.0 (Dated 28-Mar-2023)

Effective date: 29-Mar-2023

Expiration date: 29-Mar-2024

Impact of using zinc oxide versus Moist Exposed Wound Ointment (MEBO) in treatment of second stage pressure ulcer: A randomized control clinical trial.

$n= 0.5 (1-0.5) + 0.167 (1-0.167) (0.84+1.96)^2 / (0.5-0.167)^2 = 27.5 \approx 28$ patients, in addition to attrition rate 20 % therefore sample size will be 34 patients for each group.

A total number 76 patients will be included in the study. A number of eight participants will be included in the pilot study which will equal 10% of the total study number and will be excluded from the study.

Duration of the Study: 12 months in total. The enrolment will be for six months. Follow up will be for maximum 1 months for each subject. A period of 6 months will be for analysis and closing.

Setting:

This study will be carried out at medical ward, neuroscience ward, and intensive care unit at King Abdullah Medical City, Holy Makkah.

Data Collection and Management:

After the official approval from KAMC IRB and the local authority approval. The principal investigator will have a meeting with the team for study implementation overview to ensure the quality and compliance. Researcher will explain the study to the participants and take written consent if they want to participate. For unconscious patient written approval will be taken from there Legally Acceptable Representative. The participation will be voluntary and anonymously. In case of passing away the collected data will not be used and safety reports will be submitted as per the local gaudiness. In case of discharge the collected data will not be used and the patient will be excluded. All data collection sheets will be kept in a locked file cabinet with the researchers.

- 10 -

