Short Title: Impact of using Zinc Oxide versus Moist Exposed Wound Ointment (MEBO) in treatment of second stage pressure ulcer: A randomized control clinical trial.

Version: 5.0 (Dated 28-Mar-2023)

Effective date: 29-Mar-2023

Expiration date: 29-Mar-2024

Impact of using zinc oxide versus Moist Exposed Wound Ointment (MEBO) in treatment of second stage pressure ulcer: A randomized control clinical trial.

Study outcome measurement:

Data will be collected through one tool that will be collected by the assessor daily. It will include two sections as follows:

Section I: Patients' demographic data

This section was developed by the PI based on relevant literature. It will include demographic and medical history data will be collected from the patients' medical records without identifier such as age, sex, body mass index, history of smoking, diagnosis at the time of admission, and laboratory parameters including erythrocyte sedimentation rate (ESR) and C-reactive protein (CRP) will be recorded. Nutritional status of patients will be evaluated considering route of nutritional support (enteral or parenteral). Subject will be identify via serial codes.

Section II: Pressure ulcer assessment.

This section will be adopted from Bates-Jensen 2010 [31]. The Bates-Jensen Wound Assessment Tool (BWAT) will be used to evaluate wound healing. It is a validated wound assessment tool which is used in many healthcare settings for wound assessment. BWAT is straight forward to use and allows nurses to have an objective, comprehensive assessment of wounds. It consists of 13 items to evaluate wound size, type and depth, amount of necrotic tissue, amount and characteristics of exudate, the presence of granulation tissue, epithelialization, and peri- 6 wound skin. PU length and width was measured with a disposable ruler and expressed as cm². Patient will be examined daily till complete healing for the pressure ulcer and maximum one month. If the pressure ulcer not healed within the month of the treatment duration this patient will return to routine care of the hospital. If the any patient will be unable to continue the study because of death, discharge, or change in the care setting the researcher will be excluded from the study.

Each item is graded on a scale of 1 to 5, where a score of 1 indicates progress toward healing while a score of 5 indicates the absence of healing or wound deterioration. Cumulative BWAT scores vary

- 11 -

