Short Title: Impact of using Zinc Oxide versus Moist Exposed Wound Ointment (MEBO) in treatment of second stage pressure ulcer: A randomized control clinical trial.

Version: 5.0 (Dated 28-Mar-2023)

Effective date: 29-Mar-2023

Expiration date: 29-Mar-2024

Impact of using zinc oxide versus Moist Exposed Wound Ointment (MEBO) in treatment of second stage pressure ulcer: A randomized control clinical trial.

from 13 to 65. The English version of BWAT has been reported to have good reliability (Cronbach alpha=0.91 and an interrater reliability coefficient of 0.99).

The ulcer status will be completed by the assessor when the pressure ulcer healed or the end of the month, the ulcers will be examined blindly and assessed as “Completely Healed,” “Partially Healed,” “Without Improvement,” or “Worsening.”. “**Completely healed**” was defined as an intact dermis and epidermis, and no abrasion or ulceration. “**Partially healed**” was defined as any decrease in ulcer size compared with the baseline ulcer tracing but excluding complete healing. “**Without improvement**” was defined as no change in ulcer size compared with the baseline ulcer tracing. “**Worsening**” was defined as any increase in ulcer size compared with the baseline ulcer tracing. Duration of treatment will be record at the assessment sheet.

Statistical Analysis Plan

Data obtained from the study will be coded and transformed into coding sheets. The results will be checked. Then, the data will be entered into SPSS system files (SPSS package version 22). Following data entry, checking and verification process will be carried out to avoid any errors during data entry. Finally, analysis and interpretation of data will be conducted. Categorical variables will be expressed as number and percentage while continuous variables will be expressed as mean and standard deviation.

Publication:

The results of this research will be published to either national or international publications. The main credit in publication will go to King Abdullah Medical City in Holy Capital and to the principal investigator and co-investigators. Others who have contributed less substantially will have an acknowledgement in the manuscript.

Ethical Part & Confidentiality:

- 12 -

Short Title: Impact of using Zinc Oxide versus Moist Exposed Wound Ointment (MEBO) in treatment of second stage pressure ulcer: A randomized control clinical trial.

Version: 5.0 (Dated 28-Mar-2023)

Effective date: 29-Mar-2023

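### The only data tool described has no adverse-event record, so one ointment could be called superior with no by-arm account of harms

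*Protocol*

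**What the plan says.** All references are to the protocol.

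- **Study outcome measurement.** The opening statement is: "Data will be collected through one tool that will be collected by the assessor daily. It will include two sections as follows". The first of these covers demographics, history and route of nutrition, and adds that "laboratory parameters including erythrocyte sedimentation rate (ESR) and C-reactive protein (CRP) will be recorded", without saying when. The second is the 13-item BWAT, whose listed content includes "amount and characteristics of exudate, the presence of granulation tissue, epithelialization, and peri- 6 wound skin".
- **Ulcer status**, end of the same section. At healing or at month end a blinded assessor grades the ulcer. The Worsening grade "was defined as any increase in ulcer size compared with the baseline ulcer tracing". Duration of treatment is recorded; a reason for its ending is not mentioned.
- **Data Collection and Management.** On death: "In case of passing away the collected data will not be used and safety reports will be submitted as per the local gaudiness". A separate sentence deals with patients who leave hospital: "In case of discharge the collected data will not be used and the patient will be excluded".
- **Exclusion Criteria.** Entry is closed to "Patients with suspected hypersensitivity reactions to any of the topical formulation's ingredients", and to patients with signs of wound infection (pus, odour, tenderness, heat, redness, fever).
- **Objectives.** Efficacy is primary and recovery time is secondary. There is no safety objective. The rationale just before says that the trial will "determine which one is superior to other".

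**The concern.** The protocol sets out what will be collected as a complete list: one tool with two sections. Nothing on that list is an adverse-event record. How harms are summarised can be left to an analysis plan, but whether they are written down cannot, because events not recorded during the month of treatment cannot be analysed later.

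At stake is the basis for preferring one ointment. A contact reaction around the wound would enter the data only as a worse peri-wound skin item inside a total healing score, and would be read as slower healing. A patient whose ointment was stopped for a reaction would have a treatment duration and no reason. A patient who then died or was discharged would have no usable data at all.

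**Working it through.** **Step 1. What could carry a signal of harm, and what each item lacks.**

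| Recorded item | Where | Limit as a record of harm |
|---|---|---|
| Exudate, peri-wound skin (daily) | Section II, BWAT | Components of a 13 to 65 healing score; no attribution to a reaction or infection |
| ESR, CRP | Section I | Timing not stated; listed with background data |
| Worsening | Final ulcer status | Increase in ulcer size only, judged once |
| Duration of treatment | Assessment sheet | No reason for ending |
| Safety reports | Sentence on death | Sent under local guidelines; that patient's study data are not used |

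The listed fields include none for an adverse event, an application-site reaction, a diagnosed wound infection, or the reason for stopping the ointment.

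**Step 2. Who leaves the data set.** Death and discharge remove a patient's data (Data Collection and Management). A change in care setting also excludes the patient (Exclusion Criteria, Study Procedure, Study outcome measurement). If a harm contributes to any of these, its indirect BWAT trace goes too.

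**Step 3. The plan's own sample size.** With p1 = 0.5, p2 = 0.167 and C = (0.84 + 1.96)² = 7.84:

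n = [0.5 × 0.5 + 0.167 × 0.833] × 7.84 / (0.333)² = 27.51, rounded up to 28. Then 28 × 1.2 = 33.6, rounded up to 34 per group, and 2 × 34 + 8 pilot patients = 76. The protocol's figures reproduce.

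**Step 4. What a harms record could show at that size.** The protocol gives no event rates, so the rates below are assumptions. The chance of at least one event among n treated patients is 1 − (1 − r)^n.

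| Assumed rate r | n = 34 | n = 28 |
|---|---|---|
| 1% | 29% | 25% |
| 2% | 50% | 43% |
| 5% | 1 − 0.95^34 = 83% | 76% |
| 10% | 1 − 0.90^34 = 97% | 95% |

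The n = 28 column is what remains if patients lost to the planned attrition are dropped. If no event is seen in 34 patients, the one-sided 95% upper bound on the rate is 1 − 0.05^(1/34) = 8.4%; with 28 it is 10.1%.

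**Step 5. What it could not show.** These are probabilities of seeing an event in one arm, not of separating the arms. At 5% against 10% with 34 per arm, power at the two-sided 5% level is about 12% by normal approximation and 3% by Fisher's exact test. At 5% against 20%, Fisher's exact test gives 31%.

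**The case against.** Several objections are sound and limit the point.

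- **Some harm is recorded.** A reader might infer that the trial is blind to local harm or infection. It is not. Exudate, peri-wound skin, ESR/CRP and Worsening all carry some signal, and the ulcer assessment is blinded in both arms. Pus and redness, two of the six infection signs listed at entry, plausibly fall under exudate and peri-wound skin. These signals are indirect and unlabelled.
- **Not stated as ointment risks.** A reader might infer that the protocol names hypersensitivity and infection as risks of the ointments and then ignores them. Both appear as entry exclusions, and infection prevention also appears as the reason for a cleaning step common to both arms.
- **Safety reporting limited to deaths.** This too is an inference. Safety reports are mentioned only beside death, but the sentence refers to local rules and does not say that other events go unreported. The opening text and consent pages were not available to this review, and safety wording there cannot be ruled out.
- **BWAT items.** The protocol says there are 13 items and summarises them without reproducing the form, so it cannot be asserted that any particular infection sign is missing from it.
- **Superiority wording.** It stands in the rationale. The formal objectives claim efficacy and recovery time only.
- **Small numbers.** Step 5 shows that recording harms would not reliably stop an ointment with more reactions from being preferred.

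None of this supplies a by-arm record of adverse events. An item inside a healing score does not separate a reaction from slow healing, and the exclusion rules remove the patients in whom a serious harm is most likely to be found.

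**Conclusion.** The point holds in limited form. The only data tool described has no field for adverse events, application-site reactions, diagnosed wound infection or the reason for stopping the ointment, and patients who die or are discharged lose their data. As written, the trial could call one ointment superior with no by-arm record of harms.

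The size of the loss is descriptive. Recording would show reactions that are common: 83% and 97% chances of at least one event in an arm of 34, at assumed rates of 5% and 10%. It would not give a reliable comparison, and rare events would usually be missed (29% at 1%). These figures assume that all 34 patients per arm are treated and their events recorded.

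The plan should be changed, because the gap is cheap to close before enrolment and largely unrecoverable afterwards. It does not invalidate the efficacy comparison.

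**What to change.** 1. **Study outcome measurement:** add a third, dated section to the daily sheet. It should cover local reaction at the application site; each infection sign already listed in the exclusion criteria; study ointment interrupted or stopped, with the reason; and any other adverse event, with seriousness. The research nurse who applies the ointment completes it, which keeps reaction reports away from the blinded assessor.
2. **Data Collection and Management:** state that safety reporting under local guidelines is not limited to deaths.
3. **Analysis:** tabulate counts and percentages by arm for everyone who received at least one application, up to last contact, including those who die, are discharged or change care setting. Amend the sentences that discard their data so that they do not apply to harms.

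The cost is one page on an existing form, one table and a few minutes per patient-day; the nurse already attends twice daily. The main drawback is that this nurse cannot be blinded, so subjective reactions will be recorded with knowledge of the arm. The counts should therefore be presented as descriptive, without a between-arm test. The change concerns recording and reporting only, and leaves treatment and its stopping untouched.

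### The three unhealed final-status grades depend only on ulcer area, so an ulcer that deepens or becomes more necrotic without growing is graded as unchanged or partly healed

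*Protocol*

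**What the plan says.** The Protocol's section on study outcome measurement sets four final grades. Timing is fixed as follows: "The ulcer status will be completed by the assessor when the pressure ulcer healed or the end of the month". The grades work like this:

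- The best grade, 'Completely healed', rests on restored skin and not on size. Its text reads: "was defined as an intact dermis and epidermis, and no abrasion or ulceration".
- An ulcer that has shrunk without closing falls under 'Partially healed', with this wording: "was defined as any decrease in ulcer size compared with the baseline ulcer tracing but excluding complete healing".
- An ulcer whose size equals that on the first tracing is 'Without improvement'.
- An ulcer that has grown is graded 'Worsening', and the rule here reads: "was defined as any increase in ulcer size compared with the baseline ulcer tracing".

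Under Section II (Pressure ulcer assessment), size is measured in the plane of the skin: "PU length and width was measured with a disposable ruler and expressed as cm²". The same section describes BWAT more broadly: "It consists of 13 items to evaluate wound size, type and depth, amount of necrotic tissue, amount and characteristics of exudate". The Objective measures section names daily BWAT as the measure for the primary objective. The status grade is not listed there under either objective.

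The Exclusion Criteria bar patients with a deeper ulcer at entry: "Either a category III or IV pressure ulcer". Deep tissue injury and signs of wound infection are also entry exclusions.

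**The concern.** Three of the four grades look at one dimension of the wound only. The protocol enrols stage II ulcers and treats deeper categories as a different and more serious state, yet no grade mentions depth, category or necrotic tissue. A wound can change for the worse in depth while its opening stays the same or shrinks, and the written rule then gives it a neutral or favourable label.

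The error runs one way: an ulcer that has deteriorated is graded better than it is, never worse. If such deterioration were more frequent with one ointment, a table of the four grades, or a combined complete-plus-partial proportion, would understate the difference or credit part of it as benefit. Measurement precision is not the cause. A perfect tracing gives the same grade.

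**Working it through.** No figure in the protocol states the size of this problem, so the check consists of applying the definitions case by case.

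**Step 1. Does 'size' include depth?** No. The grade is made against a baseline tracing, which is planar, and the measurement is length and width in cm². Section II also lists depth among the things BWAT evaluates, separately from size.

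**Step 2. Does another rule remove or re-grade such an ulcer?** No. The stated reasons for leaving the study are death, discharge and change of care setting (Exclusion Criteria, Study Procedure and Section II). Reaching category III/IV after enrolment is not among them, so the patient stays and is graded at the end of the month. Nothing links BWAT to the grade.

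**Step 3. Apply the rule.**

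| State at the status assessment | Grade as written | Grade under the fix below |
|---|---|---|
| Skin intact | Completely healed | Completely healed |
| Area smaller, depth and necrosis no worse | Partially healed | Partially healed |
| Area smaller, category III/IV or BWAT depth or necrosis worse | Partially healed | Worsening |
| Area unchanged, depth and necrosis no worse | Without improvement | Without improvement |
| Area unchanged, category III/IV or BWAT depth or necrosis worse | Without improvement | Worsening |
| Area larger | Worsening | Worsening |

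Only the third and fifth rows change.

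**Step 4. Which comparisons are affected?**

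- Complete healing, yes or no: none of the changed rows is involved, so the effect is zero.
- Complete plus partial healing against the rest: the third row is counted as a success. The fifth row is a failure under either grading. If m1 and m2 are the proportions of each arm in the third row, the observed difference is (true difference) + (m1 − m2). Equal proportions raise both arms and leave the difference unchanged. Unequal proportions bias it in favour of the arm with more deepening.
- Comparison of all four levels: both rows are misplaced.

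**Step 5. Can m1 and m2 be given a value?** No. The protocol reports no rate of progression in enrolled ulcers, and no rate of progression without growth in area.

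**Step 6. Can the sample size calculation supply a yardstick?** Its arithmetic reproduces: (0.5 × 0.5 + 0.167 × 0.833) × (0.84 + 1.96)² / 0.333² = 0.3891 × 7.84 / 0.1109 = 27.5, so 28, and 28 × 1.2 = 33.6, so 34 per group. The section does not name the outcome to which 0.5 and 0.167 refer. If it is complete healing, this point does not touch the power. If it is complete plus partial healing, it does, by an unknown amount.

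**The case against.** The strongest reply is that the deterioration is not lost. BWAT is the measure for the primary objective, it is scored daily, and it covers depth, necrotic tissue and exudate. The status grade is a supplementary label, the protocol nowhere says that partial and complete healing will be combined, and its analysis section promises only numbers and percentages for categorical variables. All of this stands and limits the reach of the point. It does not make the grade correct, because the protocol itself fixes the definitions and they will be tabulated as written.

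Four stronger readings are tempting, and the document does not support them:

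- *That the whole status outcome is graded on size alone.* 'Completely healed' is defined by intact skin.
- *That BWAT and the status must contradict each other.* BWAT is a sum of 13 items. If area falls, the size item may fall while depth rises, so the total need not rise. The individual items show the deterioration; the total may not.
- *That the effect is a few patients against a planned difference of about 11.* Assuming that 5% to 15% of 34 patients progress gives 1.7 to 5.1 per arm, and 0.333 × 34 is 11.3. The rate is only an assumption. A patient is misgraded only if the ulcer deteriorates, does not grow in area and is present for the final grading, which is a smaller and unknown fraction. The 34 includes the attrition allowance (0.333 × 28 is 9.3), and the outcome behind 0.333 is not named. The comparison carries no weight.
- *That infection and deep tissue injury should go into 'Worsening' as the Exclusion Criteria describe them.* Those are entry criteria. They include drainage, discoloured intact skin and fever. Discoloured intact skin could overlap with 'Completely healed', and fever is non-specific in a trial that enrols intensive care patients. Several of the signs are not among the BWAT contents that Section II lists, so it cannot be said that they are already recorded.

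**Conclusion.** The point holds in a narrow form. Followed as written, the three unhealed grades place an ulcer that has deepened to category III/IV, or whose BWAT depth or necrotic-tissue items have deteriorated, in 'Partially healed' or 'Without improvement' whenever its area has not grown. No other rule in the protocol prevents this.

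The primary BWAT measure and a complete-healing proportion are unaffected. A four-level comparison, or a proportion that combines complete and partial healing, is affected. Neither the number of patients nor the loss of power can be computed, and the direction of any bias between arms depends on which arm has more deterioration of this kind. The textual reading is certain; the practical impact is unknown and may be small. The change is nevertheless worth making, because it is cheap and the definition belongs to the protocol rather than to a later analysis document.

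**What to change.** Redefine the unhealed grades as follows, and leave 'Completely healed' as it is:

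- 'Worsening': an increase in ulcer size, or, in an ulcer that is not completely healed, progression to category III/IV or deterioration from baseline in the BWAT depth or necrotic-tissue items at the status assessment, whatever the area.
- 'Partially healed' and 'Without improvement': the present size rules, limited to ulcers with none of these.

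Report new wound infection by arm as a separate item, and do not build the entry list of signs into the grade.

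The cost is a wording change and one field for ulcer category on the assessment sheet. Depth and necrotic tissue are already scored in BWAT. The percentage graded 'Worsening' may be slightly higher in both arms. The change concerns outcome classification only and alters no treatment rule.
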